The secondary endpoint of percentage of subjects who experience flare will be analyzed analogously to the primary endpoint. Multiple imputation will be used to impute data for subjects with missing data. Subjects with missing AN counts at any scheduled visit (Week 4, Week 8, Week 12 and/or Week 16) will have their AN counts imputed (separately) for each visit with missing data. The imputed counts will be summed and compared to criteria for flare. If the observed or imputed value at any visit meets the definition of flare, the subject will be counted as having a flare; otherwise, the subject will be counted as not having a flare. A total of 100 imputations will be imputed to form the complete data set with a pre-specified seed (3617627) to ensure reproducibility. The final inference on treatment difference is conducted from the multiple datasets using Rubin's combining rules. Other imputation, fully conditional specification method may be implemented if the multiple imputation model does not converge.

The secondary endpoint of percentage of subjects with baseline Hurley Stage II who achieved AN count of 0, 1, or 2 will be analyzed analogously to the primary endpoint. Subjects who have missing data at Week 16 or who received an oral antibiotic that could impact HS will be included in the analysis with NRI (did not achieve AN count of 0, 1, or 2). Only subjects with Hurley Stage II at baseline will be included in the hypothesis test for AN count, while other subjects will be summarized, and a p-value reported for descriptive use only.

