10.7. Lesion Count

Lesion counts ^a	Abscess	Non- draining fistula	Draining fistula	Non- inflammatory nodule	Inflammatory nodule	Hypertrophic scar	Longest distance (mm) between 2 relevant lesions ^b	Intervening normal appearance tissue (yes or no) ^c
Left axilla								
Right axilla								
Left sub/inframammary								
Area								
Right								
sub/inframammary area								
Intermammary area								
Left buttock								
Right buttock								
Left inguino-crural fold ^d								
Right inguino-crural fold ^d								
Perianal								
Perineal								
Upper back and neck								
Other								
Totals	1 1					-		

^a Lesion counts are to be recorded every study visit.

^b If only 1 lesion, record diameter of that single lesion.
^c Are all lesions in this area clearing and separated by normal-appearing tissues? Answer: yes or no.

^d Includes the immediate adjacent area.

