6.6.5. Exploratory Analysis

Exploratory endpoints will be analyzed analogously to primary and secondary endpoints with the same strategies for ICEs. Binary endpoints will be analyzed with a stratified test of risk difference and continuous endpoints will be analyzed with an MMRM model in general. Continuous data at timepoints before and including the primary timepoint will use all data from planned assessments up to and including the primary timepoint; continuous data after the primary timepoint will use all data from all planned assessments. Visit week, treatment group and interaction will be included in the MMRM model.

The number and proportion of subjects for binary endpoints in each treatment group will be reported, along with p-values, 95% CI without strata calculated using asymptotic Wald method will be reported as well. Results for continuous endpoints will presented as LS mean changes and associated SEs with associated 95% CI and p-values. For binary endpoints, a line plot showing the proportion of subjects experiencing such endpoints will be produced. For continuous endpoints, a line plot showing the LS mean and SE for each treatment group will be produced. Exploratory endpoint results will also be listed.

The following binary endpoints before or on Week 16 will be analyzed analogously to the primary endpoints of HiSCR75 at Week 16. The number and proportion of subjects for binary endpoints in each treatment group, p-values, 95% CI without strata calculated using asymptotic Wald method will be reported as well. The binary endpoints after week 16 will include number and proportion along with Clopper-Pearson 95% CI without strata according to the four randomized treatment groups. No p-value will be reported.

- HiSCR50, HiSCR75, HiSCR90 and HiSCR100 at Weeks 2, 4, 8, 12, 24 and 32;
- AN count of 0, 1, or 2 at Weeks 4, 8, 12, 24, and 32 among subjects with baseline Hurley Stage II;

- HS flares through Weeks 4 and 32;
- IHS4-55 response rates at Weeks 4, 8, 12, 16, 24 and 32;
- Draining fistula count of 0 at weeks 4, 8, 12, 16, 24 and 32
- Draining fistula count of 0 at weeks 4, 8, 12, 16, 24 and 32, among subjects with baseline draining fistula count of at least 1
- Draining fistula count of 0 at weeks 4, 8, 12, 16, 24 and 32, among subjects with baseline draining fistula count of at least 2

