- Proportion with at least 3 points reduction from baseline in NRS in Patient Global Assessment of Skin Pain at its worst, among subjects with baseline NRS ≥ 4, at weeks 4, 8 12, 24 and 32. NRI will be handled analogously to the corresponding secondary endpoint analysis.
- \geq 50% reduction from baseline in total inflammatory lesion count (abscesses + inflammatory nodules + draining fistula) at Weeks 4, 8, 12, 16, 24 and 32
- \geq 50% reduction from baseline in draining fistula count (draining fistula alone)
- No increase in abscesses from baseline at Weeks 4, 8, 12, 16, 24 and 32

The following continuous endpoints before or on Week 16 will be analyzed with an MMRM model as specified in sec 6.6.4. LS mean changes and associated SEs with associated 95% CI and p-values will be presented. Model will include all data up to Week 16. The following continuous endpoints after Week 16 will be reported at all collected timepoints and be summarized according to the four randomized treatment groups. Mean values, mean changes and associated descriptive statistics along with 95% CI (for change from baseline) according to the four randomized treatment.

- Change of Modified Sartorius Score from baseline, Weeks 4, 8, 12, 16, 24, and 32;
- Change in PGA of Skin Pain (at its worst and average respectively) from baseline to Weeks 4, 8, 12, 16, 24, and 32;
 - If a subject received certain prohibited analgesic therapy within 28 days of the visit (including the day of the visit), the subject will be imputed as a non-responder (PGA of Skin Pain = 10) due to the ICE at the visit.
- Change in draining fistula count at Weeks 4, 8, 12, 16, 24 and 32;
- Change from baseline to Week 16 in EQ-5D;
- Change from baseline to Week 16 in DLQI;
- Change from baseline to Week 16 in HADS, HADS-anxiety, and HADS-depression;
- Change from baseline in IHS4 scores at Weeks 4, 8, 12, 16, 24, and 32

HS-PGA is an ordinal scale, as defined as below,

- Clear: No inflammatory or non-inflammatory nodules
- Minimal: Only the presence of non-inflammatory nodules

- Mild: < 5 inflammatory nodules or 1 abscess or draining fistula and no inflammatory nodules
- Moderate: < 5 inflammatory nodules or 1 abscess or draining fistula and ≥ 1 inflammatory nodules or 2 to 5 abscesses or draining fistulas and < 10 inflammatory nodules
- Severe: 2 to 5 abscesses or draining fistulas and \geq 10 or more inflammatory nodules
- Very severe: > 5 abscesses or draining fistulas

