- The following binary endpoints will be analyzed analogously to the primary endpoint by randomized treatment group. The number and proportion of subjects for binary endpoints in each treatment group, 95% CI without strata calculated using asymptotic Wald method will be reported as well.
 - HiSCR50, HiSCR75, HiSCR90 and HiSCR100 calculated with respect to Day 1 at weeks 24 and 32;

HiSCR50, HiSCR75, HiSCR90 and HiSCR100 calculated with respect to Week 16 at weeks 24 and 32

HiSCR50/75/90/100 with respect to Week 16 is defined as meeting all three criteria below:

- (AN count at Week 16 AN count at current visit) / AN count at Week 16 \times 100% \geq 50/75/90/100%
- Abscess count at Week $16 \ge$ abscess count at the current visit
- Draining fistula count at Week 16 ≥ draining fistula count at the current visit
- AN count of 0, 1, or 2 at weeks 24 and 32 among subjects with baseline Hurley Stage II;
- AN count of 0, 1, or 2 at weeks 24 and 32 among subjects with Week 16 Hurley Stage II;
- HS flares from week 16 through 32, where HS flare is defined as proportion meeting the following two criteria at any assessment after Week 16 and at or before Week 32:
 - (AN count at current visit- AN count at Week 16) / AN count at Week $16 \times 100\% \ge 25\%$
 - AN count at current visit- AN count at baseline ≥ 2
- IHS4-55 response rates at weeks 24 and 32;
- Draining fistula count of 0 at weeks 24 and 32
- Proportion with at least 3 points reduction from baseline in NRS in Patient Global Assessment of Skin Pain at its worst, among subjects with Week 16 NRS ≥ 4, at weeks 24 and 32
- Descriptive MMRM analyses will be performed by randomized treatment group, for the continuous endpoints described below. The measured value at the visit will be used as the response variable, with visit week, treatment, and treatment * visit week interaction included as predictors. The model will include all visits from Day 1

through Week 32. Estimated LSMean, corresponding SE values, and 95% confidence intervals will be summarized. Line plots by treatment group will be produced:

- NRS Patient Global Assessment of Skin Pain (WORST). To maintain consistency between all visits, only the score collected on the visit day will be used for this analysis.
- Draining fistula count, Modified Sartorius Score, IHS4 Score, HS-PGA score, all HADS scores (Total, Anxiety, Depression), EQ-5D Utility Score and DLQI Total Score.

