Appendix 1: Document History

Appendix 2: End Points Definitions and Scoring Method Modified Sartorius Score⁸

The modified Sartorius score includes an assessment of the anatomical regions involved, the numbers and scores of lesions for each region, the longest distance between 2 relevant regions (or size of a single lesion), and whether all lesions are separated by normal skin (yes or no). The detailed scoring is as following:

Each region will score as:

Item No	Items	Scoring Rules	Points	Score:
1	Anatomical region	If the region is affected	3	
		If the region is not affected, the score for that region is 0, and no further calculations are needed for the region. If the region is affected, the following are added in addition to the 3 points for the region in line 1 above.		
	For each affected region:			
2	Nodules (Inflammatory)	Count from this region	1	$1 \times \text{count}$
3	Fistulae (Draining only)	Count from this region	6	$6 \times \text{count}$

4	Longest distance between two relevant lesions within a region or size of the lesion if single	< 5 cm	1	
		5 - 10 cm	3	
		> 10 cm	9	
5	Lesions separated by normal skin?*	Yes	0	
		No	9	
	Score for the region			Sum of above

* If Lesions separated by normal skin = "No" and/or Hurley Stage = "STAGE III" then 9 points is added for the region.

Score for each region is (if the region involved) = $3 + (number of inflammatory nodule) \times 1$ + {(number of draining fistula) × 6 + {0 < (The longest distance between two relevant lesions [or size of lesion if single]) <5} × 1+ {5≤(The longest distance between two relevant lesions [or size of lesion if single]) ≤ 10} × 3 + {(The longest distance between two relevant lesions [or size of lesion if single]) > 10} × 9 + (all lesions separated by normal skin = Yes or Hurley Stage = "STAGE III") × 9

Modified Sartorius score is the sum of the score of each region. Any region with no involvement will have a score of zero for purposes of calculating the modified Sartorius score.

A region is considered "affected" if any of the following conditions are true:

- Abscess Count > 0 OR
- Any "Interventions needed" questions response = YES
- Any "Interventions needed DATE" question is not missing.
- Any "How many lesions had intervention" question > 0
- Any "How many lesions had intervention AND are no longer present" > 0
- Non-draining fistula count > 0
- Draining fistula count > 0
- Non-inflammatory nodule count > 0

- Inflammatory nodule count > 0
- Hypertrophic scar > 0

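### Two exploratory SAP derivations conflict with the plan's own definitions (a reversed modified Sartorius term and a mixed-reference post-crossover flare), and two minor exploratory items need tidying

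*SAP*

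**What the plan says.** **Modified Sartorius (SAP Appendix 2).** Item 5 of the scoring table gives 0 points if lesions are separated by normal skin and 9 if they are not. Its footnote says that if separation is No and/or the stage is III, "then 9 points is added for the region". The single-line formula below the table awards the 9 points on the condition "all lesions separated by normal skin = Yes or Hurley Stage" III.

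**Flare after crossover (SAP 6.6.7).** For placebo subjects who received izokibep in Period 2 and still had an AN count of at least 5 at Week 16, "HS flare is defined as proportion meeting the following two criteria at any assessment after Week 16 and at or before Week 32". The first criterion is a rise of at least 25% from the Week 16 count. The second is a rise of at least 2 from the baseline count.

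**HiSCR at Week 2.** SAP 6.6.5 lists "HiSCR50, HiSCR75, HiSCR90 and HiSCR100 at Weeks 2, 4, 8, 12, 24 and 32". SAP 2.6 and Protocol Section 3 also include Week 2, but the SAP objectives (2.2.3) do not. The lesion-count row of the Schedule of Activities (Protocol 1.3) marks screening and Weeks 0, 4, 8, 12, 16, 24, 28 and 32. Protocol 9.3.3 takes the same view of the scheduled visits up to Week 16: "Subjects with missing AN counts at any scheduled visit (Week 4, Week 8, Week 12 and/or Week 16". The footnote to the lesion form in Protocol 10.7, however, says counts are recorded at every study visit.

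**Fistula reduction.** SAP 6.6.5 includes a response of at least "50% reduction from baseline in draining fistula count (draining fistula alone" with no restriction on the baseline count.

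**The concern.** A final SAP should yield one value per subject for each derived variable. For the Sartorius score it yields two, depending on whether the programmer works from the table or the formula, and the formula ranks regions the wrong way round: less confluent disease scores higher. Change in this score is tested by MMRM with p-values up to Week 16 (SAP 6.6.5), and its level is modelled in SAP 6.6.7.

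The flare rule is meant to show how placebo subjects do once they switch to izokibep. Its second criterion looks back past the switch to Day 1, so worsening on izokibep is not counted until the subject is also worse than at study entry. That error runs in one direction and favours izokibep.

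The two minor items would produce rows in the results that reflect the visit schedule or the baseline count rather than treatment.

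**Working it through.** **1. Sartorius item 5.** Points by table and footnote against the formula, for an affected region:

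| Separated | Hurley stage | Table and footnote | Formula | Formula minus table |
|---|---|---|---|---|
| Yes | II | 0 | 9 | +9 |
| No | II | 9 | 0 | -9 |
| Yes | III | 9 | 9 | 0 |
| No | III | 9 | 9 | 0 |

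The two agree in 2 of 4 cases, both Stage III. With `= Yes` changed to `= No` they agree in 4 of 4.

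Example: a Stage II region with 2 inflammatory nodules, 1 draining fistula and a longest distance of 6 cm. Items 1 to 4 give 3 + 2×1 + 1×6 + 3 = 14.

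- Separated: table 14 + 0 = 14; formula 14 + 9 = 23.
- Not separated: table 14 + 9 = 23; formula 14 + 0 = 14.

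Error in a subject's total at one visit = 9 × (separated non-Stage-III regions minus non-separated non-Stage-III regions), counting affected regions only.

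Change from baseline for the same region, other items constant:

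- Status unchanged: both give 0, so the error cancels.
- Not separated to separated: table 14 - 23 = -9; formula 23 - 14 = +9. The swing is 18 points and improvement is scored as worsening.
- A change in Stage III status or in whether the region is affected can also leave a 9-point error. For example, Stage III to Stage II with lesions separated throughout is -9 by the table and 0 by the formula.

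**2. Post-crossover flare.** Let B be the Day 1 count, W the Week 16 count and C the current count, with W ≥ 5.

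- As written, a flare needs C ≥ max(⌈1.25W⌉, B + 2).
- With Week 16 in both criteria, it needs C ≥ max(⌈1.25W⌉, W + 2).

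For W ≥ 5, 0.25W ≥ 1.25. Counts are whole numbers, so a 25% rise is always at least 2 lesions and ⌈1.25W⌉ ≥ W + 2. The Day 1 criterion therefore cannot add a flare. It removes one only if B + 2 > ⌈1.25W⌉, which requires B > W, that is, a count that fell on placebo.

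| Day 1 | Week 16 | Needed, Week 16 reference | Needed, as written | Rise from Week 16, as written |
|---|---|---|---|---|
| 20 | 8 | 10 | 22 | 14/8 = 175% |
| 12 | 6 | 8 | 14 | 8/6 = 133% |
| 10 | 6 | 8 | 12 | 6/6 = 100% |

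A subject at 20, then 8, then 16 has doubled on izokibep (+8 from Week 16), yet 16 - 20 = -4, so no flare is recorded.

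Enumerating all whole-number combinations (B and W from 5 to 40, C from 0 to 60) gives 42,120 flares on the Week 16 reference. The written rule misses 6,468 of them and adds none. The grid is unweighted, so 6,468/42,120 = 15.4% is not a patient rate.

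**3. Week 2 HiSCR.** If no counts are taken and missing is set to non-response, every arm has 0 responders. The risk difference is 0, its standard error is 0, and the test statistic is 0/0.

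**4. Fistula reduction.** The response needs (B - C)/B ≥ 0.50, which is undefined for B = 0. Such subjects can be enrolled: Protocol 5.1 requires no fistula, 5.2 only excludes counts above 20, and SAP 6.4.2 tabulates presence at baseline as yes/no.

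**The case against.** The best defence on Sartorius is that the table and footnote agree with each other and only the formula dissents. A reader might infer that reported scores will be wrong; the documents show a contradiction, not which text will be coded. SAP Appendix 1 says the Appendix 2 scoring rules were updated to match a verified approach, but does not say which statement was verified. A reader might also infer a 9-point error per region in the endpoint itself. The endpoint in SAP 6.6.5 is change from baseline, where a constant error cancels. Both points stand as limits on size.

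A unit error is a further tempting inference, because the form records "Longest distance (mm) between 2 relevant lesions" and the formula uses bare 5 and 10. The table states cm, so conversion is routine programming; nothing says raw mm are to be compared with those cut-offs.

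On Week 2, it would go too far to say that the data cannot exist or that every arm will show 0%. SAP 6.6.1 limits earlier HiSCR75 analyses to timepoints at which the data are collected, the Protocol 10.7 footnote calls for counts at every study visit, and Week 2 is a visit in both regimens (Protocol 4.1.2). What remains is an unreconciled visit list.

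On fistula reduction, a reader might infer that subjects with a zero baseline become failures by non-response imputation. The SAP specifies that imputation for missing assessments and certain antibiotic use, and is silent on an undefined ratio. Any dilution depends on the share with no baseline fistula, which the documents do not give. If these subjects were scored as failures, a 50% rate would show as 40%, 30% or 20% for assumed shares of 20%, 40% or 60% (50% × (1 - share)).

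None of this answers the flare rule. The word baseline there cannot mean Week 16: the same list separates baseline Hurley stage from Week 16 Hurley stage, and its HiSCR relative to Week 16 uses Week 16 in all three criteria.

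**Conclusion.** Two derivations should be corrected. The Sartorius formula contradicts its own table: 9 points per affected non-Stage-III region in level, and up to 18 points per region in change when separation status switches. This is conditional on the formula being the text that is programmed. The flare rule needs no such condition; applied literally, it can only under-count flares, and only among subjects whose count fell between Day 1 and Week 16. How many subjects that is cannot be derived from the documents.

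The Week 2 and fistula items are minor: an inconsistency to reconcile and a gap to close.

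All four are exploratory or descriptive. The flare endpoint through Week 16 uses baseline in both criteria (SAP 2.5 and 6.6.3.1) and is untouched, as are the primary and other alpha-controlled tests.

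**What to change.** 1. **SAP Appendix 2:** in the formula, change `= Yes` to `= No`. Optionally state that mm on the form are converted to cm.
2. **SAP 6.6.7:** in the second flare criterion, replace the baseline AN count with the Week 16 AN count. While that list is open, confirm that its pain item, which combines a reduction from baseline with a Week 16 score of at least 4, is intended.
3. **Week 2:** reconcile SAP 2.6 and 6.6.5, Protocol Section 3 and the Protocol 10.7 footnote with the Schedule of Activities and SAP 2.2.3. If Week 2 counts are not scheduled, drop Week 2 from the SAP lists or report it as not assessed, and do not apply non-response imputation to it.
4. **SAP 6.6.5:** restrict the 50% fistula-reduction endpoint to subjects with at least 1 draining fistula at baseline, as is already done for one of the fistula-count-of-0 analyses.

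The cost is a handful of SAP wording edits, with a check and rerun of any program already written from the old text. The SAP can be corrected without a protocol amendment. Changing Protocol Section 3 as well would be an amendment, with the ethics review described in Protocol 10.1.1.
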